##### ***4.4.2 Adverse Events***

Treatment-emergent adverse events (TEAEs) are defined as those AEs with onset after the first dose of study drug or existing events that worsened after the first dose during the study. Events reported with a partial onset date (eg, month and year are reported but the day is missing) will be classified as treatment-emergent if it cannot be confirmed that the event onset was prior to the first dose of study drug based on the available date entries.

Verbatim terms on case report forms will be mapped to preferred terms and system organ classes using the MedDRA, version 24.0.

Adverse event data will be presented in data listings by subject, treatment group, and event. Serious AEs and AEs leading to discontinuation of the study drug will be presented in separate data listings.

##### ***4.4.3 Deaths, Other Serious Adverse Events, and Other Significant Adverse Events***

The following AEs will be defined as adverse events of special interest (AESI):

- [REDACTED]
- [REDACTED]
- [REDACTED]

- [REDACTED]

All deaths during the study, including the post treatment follow-up period, will be listed by subject, to include any specifying details of the death. Serious AEs and other significant AEs, including those that led to discontinuation or interruption of the study drug and AESIs, will be provided in separate subject data listings.

#### **4.4.4 Clinical Laboratory Evaluation**

All presentation of laboratory results will be based on data analyzed by the central laboratory and presented in Système International (SI) units, as suggested by the Center for Biologics Evaluation and Research and the Center for Drug Evaluation and Research *Position on Use of SI Units for Lab Tests* (Oct 2013). All data will be included in by-subject data listings. Laboratory measurements identified as abnormal (ie, outside the normal range) will also be listed separately by subject, laboratory test, and unit. In addition, normal ranges provided by the central laboratory will be presented in a separate listing.

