17.1.2. Procedures

17.1.2.1. Guidelines for Evaluation and Follow-up Testing of Mild Liver Enzyme Elevations

Guidelines for evaluation and follow-up testing of mild liver enzyme elevations (ALT or AST $\geq 3 \times$ ULN but $< 5 \times$ ULN without bilirubin elevations) include:

- A review of symptoms, history, and physical examination to assess for signs of liver enzyme elevation etiology, and updates to the CRF should be made as appropriate (see [Section 17.1.3](#)).
- Repeat ALT, AST, bilirubin, and ALP testing, and perform initial gamma-glutamyl transferase (GGT) testing, *within 1 week* with the central laboratory to confirm the results.
 - In cases in which the central laboratory is not immediately available (e.g., if the logistics are such that the participant's repeat specimen would not reach the central laboratory in a reasonable timeframe), ALT, AST, and bilirubin (total and direct) will be evaluated by the local laboratory and results will be made available to the investigator and to Alkahest as soon as possible.
- If elevations are confirmed on repeat testing, follow-up testing of ALT, AST, bilirubin, ALP, and GGT should be repeated at a minimum of every 2 weeks until ALT and AST values have decreased to $< 2 \times$ ULN.
- Once values reach $< 2 \times$ ULN, standard per protocol laboratory assessment is adequate.

17.1.2.2. Guidelines for Evaluation and Follow-up Testing of Moderate to Severe Liver Enzyme Elevations

Guidelines for evaluation and follow-up testing of moderate (ALT or AST $\geq 5 \times$ ULN without bilirubin elevations) to severe (ALT or AST $\geq 3 \times$ ULN with an elevation of total bilirubin $> 2 \times$ ULN) liver enzyme elevations include:

- A review of symptoms, history, and physical examination findings to assess for signs of liver enzyme elevation etiology, and updates to the CRF should be made as appropriate (see [Section 17.1.3](#)).

- Repeat ALT, AST, bilirubin, and ALP testing, and perform initial GGT testing, within 48-72 hours with the central laboratory to confirm the results.
 - In cases in which the central laboratory is not immediately available (e.g., if the logistics are such that the participant's repeat specimen would not reach the central laboratory in a reasonable timeframe), ALT, AST, and bilirubin (total and direct) will be evaluated by the local laboratory and results will be made available to the investigator and to Alkahest as soon as possible.

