#### *3.4.2.2 Laboratory Parameters*

Blood and urine samples will be collected at each study visit defined in the schedule of events (Section 15 of the clinical study protocol). Laboratory tests will include:

- Hematology: hemoglobin, hematocrit, red blood cell count, white blood cell count with differential, [REDACTED], platelets.
- Chemistry: hemoglobin A1c (HbA1c), glucose, sodium, potassium, calcium, inorganic phosphate, chloride, bicarbonate, magnesium, creatinine, aspartate aminotransferase (AST), alanine aminotransferase (ALT), alkaline phosphatase, lactate dehydrogenase, direct and indirect bilirubin, blood urea nitrogen (BUN), total protein, albumin, and eGFR.
- Serology: hepatitis B virus (HBV), hepatitis C virus (HCV), and human immunodeficiency virus (HIV).
- Coagulation: partial thromboplastin time (PTT), prothrombin time (PT).
- Urinalysis: pH, glucose, erythrocytes, leukocytes, protein, nitrites, UACR.
- Pregnancy: pregnancy testing will be performed at the site in either urine or serum; a positive test result must be confirmed by a serum pregnancy test performed by the central laboratory.

Additional laboratory parameters may be reported. Clinical evaluation of liver injury, including additional testing, may be performed as defined in Section 17.1 of the clinical study protocol. Samples may be used for re-testing, further evaluation of an AE and/or assessment, and follow-up of other exploratory endpoints.

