#### 4.1.1 *Reporting Conventions*

In general, all data collected and any derived data will be presented in subject data listings for all enrolled subjects. Listings will be ordered by site, subject number, treatment group, and assessment or event date. The treatment group presented in listings will be based upon the actual treatment received.

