#### 4.1.2 *Summarization by Visit*

All data, including unscheduled visits, will be included in subject listings.

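### Does SAP 4.4.4, by basing laboratory presentation on central-laboratory data, leave out the local liver repeats that the protocol allows?

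*SAP*

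**What the plan says.** SAP 4.4.4 sets the source for laboratory listings: "All presentation of laboratory results will be based on data analyzed by the central laboratory", in SI units. It continues: "All data will be included in by-subject data listings". Results outside the normal range are also listed separately, and "normal ranges provided by the central laboratory will be presented in a separate listing". It mentions no other laboratory.

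The protocol's liver appendix (17.1.2.1 for mild elevations, 17.1.2.2 for moderate to severe) asks for the repeat at the central laboratory. Both sections add a fallback for when that is not practicable: "ALT, AST, and bilirubin (total and direct) will be evaluated by the local laboratory and results will be made available to the investigator", and to the sponsor.

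SAP 3.4.2.2 refers to this work-up: "Clinical evaluation of liver injury, including additional testing, may be performed as defined in Section 17.1 of the clinical study protocol". Two general SAP rules also bear on the point. Section 4.1.1: "In general, all data collected and any derived data will be presented in subject data listings for all enrolled subjects". Section 4.1.2: "All data, including unscheduled visits, will be included in subject listings".

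**The concern.** A local repeat is a laboratory result that the central laboratory did not analyse. Taken at its word, the opening sentence of 4.4.4 excludes it, and the listing of normal ranges has no place for the local limits. A local value cannot be flagged as abnormal, or expressed as a multiple of the upper limit of normal, without those limits.

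The subject matter makes the omission look worse than an ordinary drafting gap. SAP section 1 says the study ended because of liver enzyme findings in other AKST4290 studies. Under SAP 4.6 the report is listings only, so no summary table or model would show the value elsewhere. The repeat also has a function. Protocol 5.6.1 ties the liver discontinuation criteria to confirmation on repeat testing, and protocol 8.2.1 does the same for the two lower liver severity grades. If the confirming number were absent, a reader of the report could not check that confirmation.

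**Working it through.** The plan gives no figure to reproduce and no formula applies. The check is a comparison of texts.

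1. **Does any SAP sentence name local results?** No. Sections 3.4.2.2, 4.1.1, 4.1.2, 4.1.3, 4.4.4 and 4.6 were compared with protocol 5.6.1, 8.2.1, 17.1.2 and 17.1.3. Section 3.4.2.2 points to the protocol's liver work-up but gives no rule on source. Section 4.1.3 covers only values reported as beyond a quantifiable limit. The factual core of the concern is right.

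2. **Does the SAP exclude them?** There are two readings.
   - *Narrow.* The sentence promising that all data are listed comes straight after the central-laboratory sentence and means all central data. Local repeats are then left out.
   - *Broad.* That sentence means what it says, in line with 4.1.1 (all data collected) and 4.1.2 (unscheduled visits included). A local repeat held in the database is an unscheduled record and is listed.

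   SAP 3.4.2.2 favours the broad reading. It counts pregnancy tests among the laboratory tests and says "pregnancy testing will be performed at the site in either urine or serum". The central-laboratory sentence therefore cannot have been written as a bar on every result from elsewhere. It reads as a convention on units and ranges for the routine panel.

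3. **What is reported on either reading?**
   - The central value that triggered the repeat, both in the by-subject listing and in the separate listing of abnormal results (SAP 4.4.4).
   - The event: protocol 8.2.1 sends confirmed elevations to the AE log, and SAP 4.4.2 and 4.4.3 list AEs, SAEs, AESIs and AEs that led to discontinuation or interruption.

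4. **What depends on the local number?**
   - Grading: in protocol 8.2.1 the mild and the at-least-moderate ALT/AST grades require confirmation on repeat. The severe grade (ALT or AST at least 3 × ULN with total bilirubin above 2 × ULN) carries no such condition, so the most serious category does not turn on a repeat.
   - Discontinuation: the confirmation rule in protocol 5.6.1 operates during treatment, on results sent to the investigator and the sponsor. SAP section 1 says active participants had to stop study drug after the notice of 09Dec2021, so the rule could have mattered only before then.
   - Inference: nothing. SAP 4.6 plans no estimate, test or summary.

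5. **How large is it?** One local repeat carries four values: ALT, AST, total bilirubin and direct bilirubin. SAP section 1 reports three participants randomised and on study drug at the time of the notice. The documents do not say whether any liver elevation or local repeat occurred among them, so any total would be four times an assumed count.

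**The case for a change.** The strongest case for a change is that 4.4.4 is the specific rule, that it governs the whole presentation of laboratory results, and that section 4.1.1 is qualified as holding only in general. Two programmers could build different listings and both comply, although SAP section 1 says the plan exists to avoid post hoc decisions. Even the broad reading brings in the value without its reference range. The AE listings are not stated to carry the number, protocol 17.1.3 names histories and not local values as CRF content, and a sentence or two would settle the matter.

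Part of this stands. The SAP does not say which reading applies and makes no provision for local ranges. The rest has less force. An analyst who found a local ALT in the database would list it with its source and its own limits; suppressing it or judging it against the central range would not be a sensible alternative. The layout of the listings, including any columns for source and range, is left by SAP 4.6 to a Data Listings Layouts document that is not available here and may already deal with this. The argument from protocol 17.1.3 is one from silence, since that section does not claim to list everything that is captured. If a local value never reached the database, rewording 4.4.4 would not put it there.

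**Conclusion.** The observation is accurate, but it does not call for a change. It is a gap in detail that the SAP's own general listing rules allow analysts to fill sensibly. The effect is confined to some rows, and the ranges beside them, in the laboratory listings of a terminated study with three participants on drug when it stopped. No estimate, test, severe-grade classification or conclusion moves.

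This rests on three assumptions: that any local repeat was entered in the database; that the phrases promising all data are read as covering it; and that the listing layouts, not seen here, do not say otherwise. If a local repeat was collected and the narrow reading was applied, the loss would be four values per repeat. The triggering central result would still be listed, and so would any adverse event recorded from the elevation.

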#### **4.4.5 Vital Signs, Physical Findings, and Other Observations Related to Safety**

##### **4.4.5.1 Vital Signs**

Vital sign parameter measurements will be provided in a listing.

##### **4.4.5.2 12-Lead Electrocardiogram**

Twelve-Lead ECG interval parameters will be provided in a listing. Twelve-lead ECG will be classified by the investigator as “normal,” “abnormal, not clinically significant,” or “abnormal, clinically significant.”

Prolonged QTc intervals will be flagged in the ECG listing as QTcF measurements (msec) that are >450 at each visit where ECG is routinely collected per the clinical study protocol.

##### **4.4.5.3 Physical Examination**

Results of the physical examination will be presented in subject data listings by subject, study visit, and body system.

##### **4.4.5.4 Slit Lamp Examination (Dilated and Undilated) and Gonioscopy**

Results of slit lamp examination and gonioscopy assessments will be presented in a listing.

##### **4.4.5.5 Extended Ophthalmoscopy**

Extended ophthalmoscopy assessments of the peripheral retina are categorized as absent (or no), present (or yes), or questionable (when available) and will be presented in a listing.

#### 4.4.5.6 *Intraocular Pressure*

Intraocular pressure (mmHg) will be presented in a listing.

#### 4.4.5.7 *Prior and Concomitant Medications and Procedures*

Medications will be coded using the World Health Organization Drug Dictionary Enhanced (WHODDE), version B3 March 2021. Medications entered on the eCRF will be mapped to Anatomical Therapeutic Chemical (ATC) drug class (level 1) and drug name.

The study phase (prior and/or concomitant status) of each medication will be determined programmatically based on medication start and end dates. A prior medication is defined as any medication administered prior to the date of the first dose of study drug. A concomitant medication is defined as any medication administered on or after the date of the first dose of study drug. A medication may be defined as both prior and concomitant. If it cannot be determined whether a medication was received prior to the start of study drug dosing due to partial or missing medication start and/or end dates, it will be considered a prior medication. Likewise, if it cannot be determined whether a medication was received after the start of study drug dosing, it will be considered concomitant.

The study phase during which each medication was received (eg, prior, concomitant, or both) will be presented on the listing of prior and concomitant medications.

Prior and concomitant procedures will be provided in a listing. The study phase during which each procedure was performed (eg, prior or concomitant) will be determined based on the reported date of the procedure using the similar logic as described for medications; if partial dates are reported for a procedure date, a procedure may be defined as both prior and concomitant. If it cannot be determined whether a procedure was received prior to the start of study drug dosing due to a partial or missing procedure date, it will be considered a prior procedure. Likewise, if it cannot be determined whether a procedure was received after the start of study drug dosing, it will be considered concomitant.

### 4.5 **Determination of Sample Size**

Due to a dearth of studies with a 3-step improvement, as well as potential variabilities between each eye, the sample size is powered on the primary hypothesis comparing the difference between treatment arms (AKST4290 and placebo) in the proportion of participants with a  $\geq 2$ -step improvement of DR severity level on DRSS score in a single eye from baseline as compared with Week 24. All calculations were based on the following fixed assumptions:

- Target 80% power.
- 2-sided alpha = 0.046.
  - It should be noted that to account for Data and Safety Monitoring Board (DSMB) interim data reviews, the alpha spending approach has been adopted using an alpha reduction of 0.001 for each review

(assuming a total of 4 reviews). The required sample size does not change if only three DSMB meetings are necessary.

- Test of 2 independent proportions based on the normal approximation.
- Based calculation on PANORAMA ([NCT02718326](#), [EYLEA Full Prescribing Information](#)), RISE/RIDE ([Nguyen 2012](#), [Wykoff 2018](#)), and VIVID/VISTA ([Korobelnik 2014](#), [Brown 2015](#)) study data.

The total sample size using the assumptions stipulated is approximately 80 enrolled participants to allow for a total of 69 completed participants. The randomization schema is 2:1 (AKST4290:placebo). Group sample sizes of 46 in the AKST4290 group and 23 in the placebo group will achieve approximately 80% power to detect a difference in group proportions of 24%. The proportion in the AKST4290 group is assumed to be 6% under the null hypothesis and 30% under the alternate hypothesis. The proportion in the placebo group is assumed to be 6%.

#### 4.6 Changes in the Conduct of the Study or Planned Analyses

This SAP has been modified to accommodate the limited number participants enrolled in this prematurely concluded study. Three study participants were randomized and taking study drug at the time Investigators were requested to discontinue the study. Given the limited data, all data will be presented in the form of listings (as described in the Data Listings Layouts document).

